## **Study Title**

**Methotrexate, blood pressure and arterial function in patients with rheumatoid arthritis**

**NCT number: TBA**

**Date of the document: March 10, 2017**

## Study protocol

### Four groups of patients will be studied:

1. Newly diagnosed RA patients started on subcutaneous MTX and studied at baseline, 1 and 6 months (n=31). Patients will be initially prescribed 10 mg subcutaneous MTX once a week. Then, the dose will be adjusted based on the response by 5 mg increments up to 25 mg a week. If required, use of steroids, NSAIDs, and/or other DMARDs is allowed during the study period.
2. Newly diagnosed RA patients started on another DMARD (sulfasalazine) and studied at baseline, 1 and 6 months (n=31). Patients will be initially prescribed 500 mg sulfasalazine daily. Then, the daily dose will be increased by 500 mg each week to a maximum of 2 g daily after 4 weeks. According to clinical response, the maintenance dose will be 2-3 g daily. If required, use of steroids, NSAIDs, and/or other DMARDs (except MTX), is allowed during the study period.
3. RA patients on chronic treatment (>1 year) with oral MTX (with or without issues with tolerability, e.g. gastrointestinal side effects) at baseline and switched to subcutaneous MTX at the same dose (studied at baseline, 1 and 6 months, n=31).
4. RA patients on chronic treatment (>1 year) with other synthetic DMARDs at baseline and continued on the same DMARDs, and their dose, at 1 and 6 months (studied at baseline, 1 and 6 months, n=31).

Groups 1 and 2: randomization to subcutaneous MTX vs. sulfasalazine will be open to both patients and rheumatologists, facilitating monitoring of response and potential side effects. However, they will be asked not to disclose their treatment to the research team.

Groups 3 and 4: this is an open observational study where group 3 patients switch their oral MTX to subcutaneous MTX, and group 4 patients continue their treatment with the same DMARDs throughout the study duration.

Study population and eligibility criteria: Adult RA patients, diagnosed according to established criteria (2010 ACR/EULAR), will be recruited from rheumatology clinics at Flinders Medical Centre (Southern Adelaide Local Health Network). Demographic and clinical characteristics and genetic polymorphisms will be assessed at baseline in newly diagnosed RA patients commencing either subcutaneous MTX (group 1) or sulfasalazine (group 2), and in RA patients already on long-term (>1 year) treatment with either oral MTX (group 3) or other synthetic DMARDs (group 4). Group 1 and group 2 (newly diagnosed RA patients) will be randomized to either subcutaneous MTX (group 1) or sulfasalazine (group 2, age- and sex-matched) in a 1:1 ratio.

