### *Inclusion criteria*

- Patient with rheumatoid arthritis according to EULAR/ACR 2010 criteria.
- Age  $\geq 18$  years.
- Written informed consent, dated and signed before initiating any study-related procedure.

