Central and 24-hr BP will be assessed using PWA (SphygmoCor, AtCor Medical, West Ryde, NSW) and Mobil-O-Graph technology (I.E.M., Stolberg, Germany) available within our group. Prior to PWA, patients will abstain from alcohol for  $\geq 12$ -hrs, and from tobacco and caffeine for  $\geq 4$ -hrs. Patients will be required to fast for  $\geq 6$ -hrs. A small probe will be placed on the radial artery, and AIx and central BP measurements will take approximately 10 min. The Mobil-O-Graph will provide a 24-h assessment of peripheral and central BP, and PWV. \

**MTX-polyglutamates PGs (MTX-PGs) and 5-MTHF:** RBCs MTX-PGs concentrations will be measured at each assessment visit with a validated LC-MS/MS assay developed at the School of Pharmacy and Medical Sciences, University of South Australia. Whole blood samples will be centrifuged, plasma removed and cells are washed two times with PBS. Packed cells are then stored at  $-80$  °C prior to analysis. Stable isotope internal standard is added to 0.25mL packed RBC and proteins are precipitated with perchloric acid. MTX-PGs are purified by solid phase extraction (Strata-X Strong Cation Exchange) prior to LC separation via HILIC LC (ZIC-HILIC Column, Merck Millipore) and analysis on a Shimadzu 8060 triple quadrupole MS/MS. This assay quantifies the five MTX-PGs commonly seen in RA patients and has a limit of detection of  $<0.2$  nmol/L packed RBCs. Whole blood and plasma 5-MHTF will be measured at each assessment visit according to a method previously published. 50 $\mu$ L of whole blood or plasma is diluted with 50 $\mu$ L of 5% ascorbic acid solution containing 10mM mercaptoethanol and 10 $\mu$ L of internal standard (stable isotope labelled 5-MHTF) and incubated at 37 °C for 60 min. 60 $\mu$ L of 10% trichloroacetic acid is added, the mixture vortexed and the clear supernatant removed. 5-MHTF is separated via reverse phased LC using a Waters Acuity BEH C18 column (100X2.1mm), and detected with a Shimadzu 8060 Triple Quadrupole MS/MS.

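### Groups 3 and 4 are defined by more than a year of treatment with no stable-dose condition, so drift from an earlier oral MTX dose change can be read as an effect of the switch

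*Combined protocol and SAP*

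**What the plan says.** All references are to the combined protocol and SAP.

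- **Entry to groups 3 and 4** (Four groups of patients will be studied). Group 3 is "RA patients on chronic treatment (>1 year) with oral MTX", with or without tolerability problems. Group 4 is "RA patients on chronic treatment (>1 year) with other synthetic DMARDs at baseline". The paragraph on study population and eligibility repeats the one-year duration and adds nothing about dose.
- **Dose rules** (same section). Group 3 patients are on oral MTX "at baseline and switched to subcutaneous MTX at the same dose". Group 4 patients are "continued on the same DMARDs, and their dose, at 1 and 6 months". Both rules look forward from baseline.
- **Inclusion and exclusion criteria.** The three inclusion items are diagnosis ("Patient with rheumatoid arthritis according to EULAR/ACR 2010 criteria"), age and consent. The nearest exclusion concerns unstable illness, not a change of DMARD dose.
- **Data collected** (Clinical, demographic and laboratory variables). Type and dose of medication are taken at baseline, 1 and 6 months. Medical history is collected, but the date and size of the last dose change are not specified items.
- **Exposure marker** (MTX-polyglutamates and 5-MTHF). "RBCs MTX-PGs concentrations will be measured at each assessment visit".
- **Analysis** (Statistical methods). Linear mixed models adjust for, among other things, medicines that may alter blood pressure with their doses, disease activity and inflammatory markers. MTX-PGs enter through the mediation analysis. Time since a dose change is not a covariate.

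**The concern.** Group 3 is informative because the route changes while the drug and the dose at the switch stay the same. A before-after comparison of that kind isolates the route only if the patient is close to steady state at baseline. A year on a drug does not ensure this: as written, a patient whose oral dose changed a week or two before baseline qualifies and is switched at the new dose. If MTX-PGs, and possibly disease activity and blood pressure, are still responding to the earlier change, the 1- and 6-month changes combine that response with any effect of the route.

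Group 4 cannot subtract this drift. It takes other DMARDs and was not formed by randomisation. Group 4 patients with a recent change of their own would bring a different drift. In the mediation analysis, MTX-PG accumulation left over from before baseline could be credited to the switch.

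**Working it through.** **1. Does any provision close the gap?**

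| Provision | What it fixes | Dose before baseline? |
|---|---|---|
| Group 3 and 4 definitions | More than 1 year on treatment | No |
| Group 3 dose rule | Dose carried over at the switch | No |
| Group 4 dose rule | Same dose at 1 and 6 months | No |
| Inclusion and exclusion lists | Diagnosis, age, consent, comorbidity | No |
| Medication data | Type and dose at three visits | No |
| Model covariates | Include doses of medicines that may alter blood pressure | No: a dose recorded at a visit carries no information on when it was last changed |

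None does.

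**2. How large could drift in MTX-PGs be?** The documents give no figure for this, so every input here is an assumption: MTX-PGs proportional to dose at steady state, first-order accumulation with half-life *h* of 3, 4 or 8 weeks, oral dose raised from 15 to 20 mg *w* weeks before baseline, and no route effect at all. On a scale where the steady-state level equals the dose:

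PG(t) = 15 + 5 × (1 − 2^(−t/h))

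The spurious change is PG(w + 4.3)/PG(w) − 1 at 1 month and PG(w + 26)/PG(w) − 1 at 6 months. Example with w = 2, h = 4: PG(2) = 16.46, PG(6.3) = 18.32 and PG(28) = 19.96, giving +11.3% and +21.2%.

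| Rise made before baseline | 1 month (h = 3 / 4 / 8) | 6 months (h = 3 / 4 / 8) |
|---|---|---|
| 1 week | 15.6 / 14.0 / 9.3% | 24.7 / 26.3 / 26.6% |
| 2 weeks | 11.8 / 11.3 / 8.3% | 18.6 / 21.2 / 23.8% |
| 13 weeks | 0.8 / 1.4 / 2.7% | 1.3 / 2.7 / 7.9% |

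A cut from 20 to 15 mg made 1 or 2 weeks before baseline gives about −17% to −22% at 6 months, so raises and cuts partly cancel in a mean. If 20% of group 3 had a raise 1 or 2 weeks before baseline and nobody had a cut, the group mean would shift by 0.20 × 18.6% = 3.7% to 0.20 × 26.6% = 5.3%, that is, about 4–5%.

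**3. What would a given drift do to the group 3 versus 4 contrast?** The plan gives n = 31 per group, without alpha, power, effect size or SD, so there is no planned figure to reproduce. Assume two-sided alpha 0.05, SD of change = 1, a simple comparison of mean changes and no drift in group 4.

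- SE = √(2/31) = 0.254 SD.
- Difference detectable with 80% power = (1.960 + 0.842) × 0.254 = 0.71 SD.
- Bias = f × d, where f is the share of group 3 with a recent change and d is their mean drift in SD units.
- False-positive rate = Φ(s − 1.96) + Φ(−s − 1.96), with s = bias/SE.

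| f | d (SD) | Bias (SD) | s | False-positive rate |
|---|---|---|---|---|
| 10% | 0.25 | 0.025 | 0.10 | 5.1% |
| 20% | 0.5 | 0.10 | 0.39 | 6.8% |
| 30% | 0.5 | 0.15 | 0.59 | 9.1% |
| 50% | 0.5 | 0.25 | 0.98 | 16.6% |

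Both f and d are assumptions. Nothing in the documents converts the percentages in step 2 into a value of d for blood pressure, augmentation index or pulse wave velocity.

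**The case against.** The strongest objection is that nothing shows the problem will occur. The documents do not say whether any group 3 patient will have had a recent dose change. At an assumed 20% share and 0.5 SD drift the bias is 0.10 SD, small beside a detectable difference of 0.71 SD. The MTX-PG illustration rests wholly on outside assumptions and does not reach the vascular outcomes. MTX-PGs are measured at every visit, and disease activity and inflammatory markers are adjusted for, which gives some protection.

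Most of this stands and limits the point. It does not remove it: the plan neither prevents nor records a recent dose change, and no sensitivity check is pre-specified, so the reader of the results could not tell which row of the table applies.

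Three stronger readings are tempting, and the documents do not support them:

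- **That drift will be reported as a switch effect.** Only the possibility follows, because frequency and direction are unknown.
- **That group 3 has more recent changes than group 4, because patients doing badly on oral MTX are the ones switched.** Group 3 admits patients with or without tolerability problems. A difference between the groups is plausible but is an inference. Gastrointestinal side effects, the example given, might as readily prompt a cut as a raise.
- **That dose adjustment fails because the group 3 dose is identical at all three visits.** The text carries the dose over at the switch; only group 4 is stated to keep its dose at 1 and 6 months. The narrower reason is enough: current dose does not encode dose history before baseline.

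**Conclusion.** The point holds in a limited form. The absence of any stable-dose condition, of a recorded last dose change and of a matching covariate can be read directly from the text. It leaves the group 3 before-after changes, the group 3 versus 4 contrast and the MTX-PG mediation path open to drift from an earlier dose change.

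The size cannot be established from the documents. Over the assumed range it runs from negligible (false-positive rate 5.1%) to material (16.6%), and the sign depends on the mix of raises and cuts. The mechanism is most direct for MTX-PGs and less certain for blood pressure, augmentation index and pulse wave velocity. The randomised comparison of groups 1 and 2 is untouched. This is a change the sponsor should make rather than a flaw that invalidates the study.

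**What to change.** 1. Add to the group 3 and group 4 definitions that the DMARD dose has been unchanged for a stated period before baseline. The sponsor should set and justify the length, since the documents give no basis for a particular figure. In the illustration a change 13 weeks before baseline still leaves 1.3–7.9% at 6 months, so the residual depends on the accumulation half-life.
2. At baseline, record the date and size of the last DMARD dose change. The plan does not currently specify this item, and it may be hard to recover later.
3. Pre-specify a sensitivity analysis of the group 3 changes and of the group 3 versus 4 contrast that excludes, or adjusts for, patients with a recent change, with "recent" defined in advance.

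If the entry condition would slow recruitment too much, items 2 and 3 alone are the minimum.

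**Cost.** A short amendment to the eligibility and analysis text, and one extra baseline data item. No visit or assay is added. The downside is that some patients enter later or are missed.

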### *Inclusion criteria*

- Patient with rheumatoid arthritis according to EULAR/ACR 2010 criteria.
- Age  $\geq 18$  years.
- Written informed consent, dated and signed before initiating any study-related procedure.

### *Exclusion criteria*

- Contraindication to MTX or sulfasalazine.
- Patient who cannot be followed during 6 months.

- Active alcohol or substance abuse within the last 12 months.
- Participation in a clinical trial within 3 months prior to the start of the study.
- Body mass index  $>35 \text{ Kg/m}^2$ .
- Secondary causes of hypertension.
- Grade 2 (moderate) or 3 (severe) hypertension: clinic blood pressure  $>160/100 \text{ mm Hg}$ .
- Resistant hypertension: clinical blood pressure  $\geq 140/90 \text{ mm Hg}$  despite concurrent use of three antihypertensive agents of different classes, one of which is a diuretic.
- Clinical systolic blood pressure  $<100 \text{ mm Hg}$  or history of symptomatic orthostatic hypotension.
- Cardiovascular event, procedure, or hospitalization for unstable angina with the last 6 months.
- Atrial fibrillation.
- Heart failure.
- Treatment with nitrates.
- Estimated glomerular filtration rate (eGFR)  $<45 \text{ mL/min}$ .
- Diagnosis of polycystic kidney disease.
- Glomerulonephritis treated with or likely to be treated with immunosuppressant drugs
- Uncontrolled diabetes with HbA1c  $>9.0\% (>75 \text{ mmol/mol})$ .
- Uncontrolled dyslipidaemia with total serum cholesterol  $>7.5 \text{ mmol/L}$  or triglycerides  $>5.6 \text{ mmol/L}$ .
- Clinical diagnosis of dementia, treatment with medications for dementia or, in the opinion of the study staff, the participant is cognitively unable to follow the protocol.
- Other medical, psychiatric, or behavioural factors that in the judgment of the study staff may interfere with study participation.
- Cancer diagnosed and treated within the past 2 years that, in the judgment of the study staff, would compromise a participant's ability to comply with the protocol and complete the study.
- Any organ transplant.
- Pregnancy, currently trying to become pregnant, or of child bearing potential and not using birth control.
- Significant illness within 2 weeks of study start.
- Patients with an unstable active medical condition that could impair evaluation of study results.

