#### *Withdrawal criteria*

- Treatment-related toxicity.
- Voluntary withdrawal from study by participant.
- Any other intercurrent medical condition or circumstance that precludes completion of the study.

**Clinical, demographic and laboratory variables:** Data collected during each study visit will include medical history, age, gender, weight, height, RA duration, DAS28, Stanford Health Assessment Questionnaire, current medications and lifestyle assessment (diet and exercise). Type and dose of medications and the following laboratory data will be collected during each assessment visit (baseline, 1 and 6 months): renal function, erythrocyte sedimentation rate, and C-reactive protein. Adverse events and adverse drug reactions will also be recorded.

**Blood pressure and arterial function:** BP, AIx (arterial wave reflection) and PWV (arterial stiffness) will be assessed at baseline, 1 and 6 months. Clinic BP will be measured in the

morning (between 9.00am and 11.00am) in a quiet, appropriate environment at room temperature, according to current guidelines, using an automated BP monitor (UA-767PC, A&D Medical) clinically validated against the British Hypertension Society protocols. Prior to BP measurement, patients will abstain from alcohol for  $\geq 12$ -hrs, and from tobacco and caffeine for  $\geq 4$ -hrs. Patients will also be required to fast for  $\geq 6$ -hrs. The arm used for BP measurement will be free of constricting clothing to avoid impediment of the cuff. The cuff will be wrapped snugly around the upper arm with the centre of the cuff bladder positioned over the brachial artery and the lower border of the cuff approximately 2 cm above the elbow bend. The cuff will be placed at heart level by supporting the arm. Patients will sit (with legs not crossed) and relax for at least 5 min, and then three BP measurements will be taken at 2-min intervals. The average of the last two BP measurements will be calculated and used in the analyses.

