### **Statistical methods**

Statistical analysis will be performed using linear mixed models. In addition to providing estimated treatment effects, this analysis will also provide estimates of the individual variability in the longitudinal changes in BP and arterial function in each of the 4 groups over time. Due to the partly observational nature of the study (group 4), models will also adjust for known potential confounders, including age, gender, co-morbidities, RA duration, 5-MTHF, drugs potentially affecting BP and their doses, DAS28, biochemical parameters and inflammatory markers. Models with and without adjustment for BP will also be assessed to test the direct and indirect effects of MTX on markers of arterial function. Similarly, we will also use mediation analysis to assess the potential direct and indirect effects of MTX-PGs, adenosine concentrations and genetic polymorphisms on the associations between MTX, BP and markers of arterial function. We will perform these analyses using Mplus software (StatModel version 7.4), which provides appropriate bootstrapping routines for estimating the non-parametric 95% CIs of indirect effects.

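### Antihypertensive treatment need not be unchanged before baseline, and the planned drug-and-dose adjustment cannot explain BP drift after a recent change; the likely effect is modest and the repair cheap

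*Combined protocol and SAP*

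**What the plan says.** The paragraph on blood pressure and arterial function makes BP a repeated outcome: "BP, AIx (arterial wave reflection) and PWV (arterial stiffness) will be assessed at baseline, 1 and 6 months". The Statistical methods section models its change and also aims at "estimates of the individual variability in the longitudinal changes in BP and arterial function in each of the 4 groups over time".

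Eligibility limits BP by level and by type of hypertension. The Exclusion criteria bar "Grade 2 (moderate) or 3 (severe) hypertension: clinic blood pressure" above 160/100 mm Hg. They also bar secondary hypertension, systolic BP below 100 mm Hg, symptomatic orthostatic hypotension, and resistant hypertension, defined as 140/90 mm Hg or more "despite concurrent use of three antihypertensive agents of different classes, one of which is a diuretic". One BP-active drug class is barred by name: "Treatment with nitrates".

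Two further exclusions leave room for judgement: "Patients with an unstable active medical condition that could impair evaluation of study results" and "Other medical, psychiatric, or behavioural factors that in the judgment of the study staff may interfere with study participation".

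The paragraph on clinical, demographic and laboratory variables lists medical history, current medications, and the type and dose of medications at each visit. It does not list the date of the last change. The Statistical methods section adjusts for "drugs potentially affecting BP and their doses".

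**The concern.** Read together, the exclusions admit two kinds of treated patient: those on fewer than three agents with clinic BP up to 160/100 mm Hg, and those controlled below 140/90 mm Hg on three. Nothing states that their regimen must have been the same for any period before baseline. The list does set look-back periods for other matters: 12 months for substance abuse, 6 months for cardiovascular events, 3 months for trial participation, 2 weeks for significant illness.

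If a drug was started, stopped or altered shortly before baseline, BP may still be moving between baseline and the later visits. That movement is counted as change during the study. In groups 3 and 4, which are not randomised, an unequal share of such patients would pass into the comparison of BP change, in a direction that cannot be known in advance. In randomised groups 1 and 2 the shares are equal in expectation, so the comparison gains variance but no expected bias. In every group the extra spread would also enter the estimates of individual variability that the plan wants.

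**Working it through.** **No plan figure to reproduce.** The protocol gives 31 patients per group without alpha, power, effect size, SD or dropout. It gives neither the share of patients on antihypertensives nor the share recently changed. Every BP figure below is therefore an assumption.

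**Inputs.** From the protocol: n = 31 per group; visits at baseline, 1 and 6 months. Assumed: a further systolic fall d of 5 to 10 mm Hg after baseline in a recently changed patient; a share p of 10% to 20% of such patients in a group; an SD of BP change of 10 mm Hg (variance 100).

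**1. Can the covariate absorb the drift?** The patient changed before baseline has the same recorded drug and dose at all three visits. With complete data, the group-by-time effect in a random-intercept model is estimated from within-patient differences, and a constant covariate drops out of those.

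A simulation shows the same. It used 300 data sets, 31 per group, 40% of patients treated, between-patient SD 8 and within-patient SD 7 mm Hg, with 20% against 5% of patients affected and d = 5:

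| Case | Without covariate (mm Hg) | With covariate (mm Hg) |
|---|---|---|
| Changed before baseline, dose constant | −0.64 | −0.64 |
| Changed after baseline, recorded | −0.77 | −0.44 |

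The expected shift in both rows is −5 × (0.20 − 0.05) = −0.75; the simulation SE is 0.13 in the first row and 0.12 in the second. The adjustment removes nothing in the first case and part of the shift in the second. With 10% affected in both groups, the randomised situation, the estimate was −0.14 (SE 0.13), consistent with no bias.

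**2. Possible bias, group 3 against group 4.** Bias = difference in p × d. For a difference of 10 percentage points (0.10 × 31, about 3 patients):
- d = 5: 0.10 × 5 = 0.5 mm Hg
- d = 10: 0.10 × 10 = 1.0 mm Hg

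**3. Size against the precision of the study.** SE of a difference in mean change = 10 × √(2/31) = 2.54 mm Hg. The bias is 0.5/2.54 = 0.20 to 1.0/2.54 = 0.39 of an SE. A two-sided 5% test would then reject a true null about 5.4% to 6.8% of the time. For comparison, the detectable difference at 80% power is 0.71 SD, or 7.1 mm Hg.

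**4. Added noise.** Extra variance = p(1 − p)d²:
- p = 0.1, d = 5: 0.09 × 25 = 2.25, so the SE grows by √1.0225, about 1%
- p = 0.2, d = 10: 0.16 × 100 = 16, so the SE grows by √1.16, about 8%

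The upper case acts like a group of 31/1.16 = 26.7 patients. It is a stretch: if 40% of a group were on antihypertensives, half of them would need a recent change.

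**The case against.** The strongest case on the other side has five parts.

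- **The plan is not silent on stability.** Hypertension under active adjustment could be treated as an unstable condition that impairs evaluation. This stands in part: staff could act case by case. But neither discretionary exclusion names antihypertensive drugs or a period, so two assessors could decide differently.
- **No reason is given why groups 3 and 4 should differ.** Both have had more than a year of treatment, come from the same clinics and face the same BP limits. This stands: imbalance is possible but not shown. A reader might infer that the BP ceiling invites treating a patient and then enrolling once BP is below it. The protocol describes no rescreening, and the ceiling applies equally to all groups.
- **The form of the drug adjustment is not fixed.** This stands. The algebra covers a main-effect term only. A recent-change-by-time term could work, but it needs a date that is not listed for collection. A reader might infer that the adjustment fails for all antihypertensive changes; that goes too far, because changes during follow-up are recorded and partly adjustable.
- **Spill-over to AIx and PWV is partly covered.** This stands: the Statistical methods section plans arterial-function models both with and without adjustment for BP.
- **The effect is small and every BP input is assumed.** This stands and sets the weight of the point.

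**Conclusion.** The gap is real. BP change is an outcome, treated non-resistant hypertensives are eligible, no criterion explicitly requires an unchanged regimen before baseline, and the data listed for collection would not identify recent changers. For those patients a main-effect drug-and-dose term cannot explain later drift.

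The consequence is modest: a possible bias of 0.5 to 1.0 mm Hg in the comparison of groups 3 and 4, about 0.2 to 0.4 of an SE, and an SE 1% to 8% larger where only noise is added. This rests on the assumed fall, share, imbalance and SD. A reader might infer that the randomised comparison is biased, or that recently changed patients should be kept out of groups 1 and 2. Neither follows, since randomisation leaves only noise and chance imbalance there. The point is worth acting on because the repair is cheap, not because the results are in serious danger.

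**What to change.** 1. **Groups 3 and 4.** Add an eligibility line requiring antihypertensive treatment to be unchanged for a stated period before baseline, and defer the baseline visit of a patient who does not yet meet it. The length of the period is a clinical decision for the sponsor.
2. **All groups.** Record at baseline the date of the last antihypertensive start, stop or dose change. Prespecify one sensitivity analysis of BP change that either excludes recent changers or includes a recent-change-by-time term, using the same period as in item 1.
3. **Groups 1 and 2.** Exclude no patient on this ground; item 2 is enough.

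**Cost.** A few deferred visits, one added question and one extra analysis. Group 3 may include patients who tolerate oral MTX poorly, so the sponsor should also state how a deferral is handled if the switch cannot wait.
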